9.6. Relationship to Study Medication

The relationship of AEs to the study medication should be assessed by the Investigator using the definitions below.

Not suspected: The temporal relationship of the event to the study medication makes a causal relationship unlikely, or, other drugs, therapeutic interventions or underlying conditions provide a sufficient explanation for the observed event.

Suspected: The temporal relationship of the event to the study medication makes a causal relationship possible or other drugs, therapeutic interventions or underlying conditions do not provide a sufficient explanation for the observed event.

If there is any valid reason, even if undetermined, for suspecting a possible cause-and-effect relationship between the study medication and the occurrence of the AE, then the AE should be considered "suspected."

If the relationship between the AE/SAE and the study medication is determined by the Sponsor to be "suspected," the event will be considered to be related to the study medication for the purposes of expedited regulatory reporting.

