### 3.5.3. Relationship to Study Medication

The relationship of AEs to the study medication should be assessed by the Investigator using the definitions below.

**Not suspected:** The temporal relationship of the event to the study medication makes a causal relationship unlikely, or, other drugs, therapeutic interventions or underlying conditions provide a sufficient explanation for the observed event.

**Suspected:** The temporal relationship of the event to the study medication makes a causal relationship possible or other drugs, therapeutic interventions or underlying conditions do not provide a sufficient explanation for the observed event.

If there is any valid reason, even if undetermined, for suspecting a possible cause-and-effect relationship between the study medication and the occurrence of the AE, then the AE should be considered "suspected."

If the relationship between the AE/SAE and the study medication is determined by the Sponsor to be "suspected," the event will be considered to be related to the study medication for the purposes of expedited regulatory reporting.

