### 3.5.4. Recording Adverse Events

Adverse events spontaneously reported by the subject and/or in response to an open-ended question from the study personnel or revealed by observation, regardless of severity or potential association with the study medication or study procedures, will be recorded in the eCRF. All AEs that occur after a subject has signed the informed consent form until the final study visit should be collected and recorded on the AE eCRF page. Adverse events will be followed until the event is resolved or stabilized, and SAEs that

are ongoing at the time of completion or discontinuation from the study will be followed until resolution.

The AE term should be reported in standard medical terminology when possible. For each AE, the Investigator will evaluate and report the following:

- Onset (date);
- Resolution (date);
- Severity grade (mild, moderate, severe);
- Relationship to study medication (not suspected, suspected);
- Action taken (none, study medication temporarily interrupted, study medication permanently discontinued, concomitant medication taken, hospitalization/prolonged hospitalization, other);
- Serious outcome (yes/no).

The severity grade should be determined by the Investigator using the definitions below:

- **Mild:** Discomfort noticed but no disruption of normal daily activity
- **Moderate:** Discomfort sufficient to cause interference with normal daily activity
- **Severe:** Incapacitating, with inability to perform normal activities

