**6. HANDLING OF MISSING DATA**

No missing data will be imputed. The reasons for missing data will be recorded.

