## **7.6. Adverse Events**

A treatment-emergent adverse event (TEAE) is one that was experienced on or after the day of first dose of OTX-101 0.09% in Study OTX-101-2016-002; or if experienced prior to first dose, worsened after first dose.

An overall summary will be presented which gives the number and percentage of subjects within each cohort that experienced a TEAE, experienced any treatment-related TEAE, permanently discontinued treatment due to a TEAE, experienced a treatment emergent SAE, and that died.

In summary tables, AEs occurring in both eyes will be summarized once at the greater intensity and relationship to study drug.

Events that are possibly or probably related will be counted as an event related to study drug.

The number and percentage of subjects experiencing one or more events within a Medical Dictionary for Regulatory Activities (MedDRA) System Organ Class (SOC) and Preferred Term (PT) class without regard to intensity, relationship, or seriousness will be tabulated by cohort. In addition, tables will display events by SOC, PT, and maximum intensity or closest relationship to treatment.

The number of deaths and SAEs will also be presented, and AEs leading to premature discontinuation from the study will be listed and tabulated.

A glossary listing that shows the verbatim terms assigned to each SOC and PT will be provided.

A listing of TEAEs by cohort ordered by subject, SOC, PT, and onset date will be provided.

A listing of serious TEAEs by cohort ordered by subject, SOC, PT, and onset date will be provided.

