**8. CHANGES FROM THE PROTOCOL**

None.

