## **10. TABLES AND LISTINGS**

### **List of Tables**

- 14.1.1 Study Performance - Safety Population
- 14.1.2 Subject Disposition - Safety Population
- 14.1.3 Visit Participation - Safety Population
- 14.1.4 Demographics – Safety Population
- 14.1.5 Inclusion and Exclusion Criteria - Safety Population
- 14.1.6 Compliance - Safety Population
- 14.1.7 Protocol Deviations – Safety Population
  
- 14.3.1.1 Treatment Emergent Adverse Events: Overall Summary - Safety Population
- 14.3.1.2 Summary of Treatment-Emergent Adverse Events by System Organ Class and Preferred Term - Safety Population
- 14.3.1.3 Summary of Treatment-Emergent Adverse Events by Closest Relationship to Study Drug - Safety Population
- 14.3.1.4 Summary of Treatment-Emergent Adverse Events by Maximum Intensity - Safety Population
- 14.3.1.5 Summary of Treatment-Emergent Adverse Events Leading to Permanent Withdrawal of Study Medication by System Organ Class and Preferred Term - Safety Population
- 14.3.1.6 Treatment-Emergent Adverse Event / MedDRA Glossary
- 14.3.2 Listing of Serious Treatment Emergent Adverse Events - Safety Population
- 14.3.3 Adverse Event Narratives
- 14.3.4 Snellen Visual Acuity - By Eye - Safety Population
- 14.3.5 Intraocular Pressure - By Eye - Safety Population
- 14.3.6 Slit Lamp Examination - By Eye - Safety Population
- 14.3.7 Dilated Fundoscopy - By Eye - Safety Population
- 14.3.8 Exposure – Safety Population

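### Does the SAP 7.6 rule for treatment-related events fail because its terms are not on the recorded causality scale?

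*SAP*

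**What the plan says.** The counting rule is in SAP 7.6: "Events that are possibly or probably related will be counted as an event related to study drug". The same section lists five items for the overall summary, among them the number and percentage of subjects in each cohort who "experienced any treatment-related TEAE". The matching output is Table 14.3.1.1, "Treatment Emergent Adverse Events: Overall Summary - Safety Population".

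What the Investigator records is set in SAP 3.5.4, with the same wording in Protocol 9.7: "Relationship to study medication (not suspected, suspected" and nothing further on that scale. Protocol 9.6 and SAP 3.5.3 define the two levels identically. An event is suspected when "The temporal relationship of the event to the study medication makes a causal relationship possible", or when other drugs, interventions or conditions do not explain it sufficiently. It is not suspected when the timing makes causality unlikely or when something else explains it sufficiently. Both sections add that any valid reason, even an undetermined one, for suspecting a possible cause-and-effect link puts the event in the suspected class.

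One sentence in those sections equates suspected with related outright. It concerns the Sponsor's determination: "the event will be considered to be related to the study medication for the purposes of expedited regulatory reporting".

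**The concern.** The counting rule names two terms, possibly and probably related, and neither is a level that the Investigator can record. The one explicit statement that suspected means related is confined to the Sponsor's view and to expedited reporting, so on its face it does not govern the tables. SAP section 8 declares no departure from the protocol, so a second scale is not announced there either.

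Taken literally, the rule finds nothing to count and the treatment-related row is zero for every cohort. Otherwise the programmer has to supply a step that the SAP does not spell out. Safety is the only objective of this extension, and the incidence of related events is a figure that readers of such a study look for. An ambiguous definition there would deserve correction if two analysts could reasonably reach different counts. That is the question to check.

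**Working it through.** No figure in the plan needs reproducing. The check is a comparison of texts and a short enumeration.

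**1. Size of the mismatch.** Terms in the rule (SAP 7.6): possibly, probably, so 2. Levels recorded (Protocol 9.7, SAP 3.5.4): not suspected, suspected, so 2. Terms in common: 0.

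**2. Reach of the rule.** The overall summary in SAP 7.6 has five items: any TEAE, any treatment-related TEAE, permanent discontinuation due to a TEAE, treatment-emergent SAE, and death. Only the second uses the relatedness rule, so 1/5 = 20% of the items. The table by SOC and PT and the table by maximum intensity do not use it. Table 14.3.1.3, by closest relationship, can be built directly from the two recorded levels.

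**3. Candidate mappings.** Each of 2 levels can be counted as related or unrelated, which gives 2 × 2 = 4 mappings.

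| Not suspected counted as | Suspected counted as | Effect on the related row | Fits the definitions? |
|---|---|---|---|
| unrelated | unrelated | always zero | No: suspected events are those with a possible causal link |
| related | related | equals the any-TEAE row | No: events judged unlikely or otherwise explained would count as related |
| related | unrelated | reversed | No, for both reasons |
| unrelated | related | subjects with at least one suspected TEAE | Yes |

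Only the last survives.

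**4. Does the text support it without the expedited-reporting sentence?** Yes. The definition of suspected rests on a possible causal relationship, which is the lower of the two terms in the counting rule. A probable relationship is stronger and falls in the same class. The instruction to class any valid suspicion of a possible link as suspected applies to the Investigator's assessment of adverse events in general. It is limited neither to the Sponsor nor to expedited reports. The two definitions can overlap, for example when timing is plausible but another explanation exists. That affects which level the Investigator chooses, and the same instruction addresses it. It does not affect how a recorded level is counted.

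**5. Whose assessment?** SAP 3.5.3 and 3.5.4 assign the assessment and its recording to the Investigator. No other relationship variable is listed for collection, so the tables have one source.

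**6. Events in both eyes.** SAP 7.6 counts these once, at the greater relationship. With two levels the greater is suspected, so no further rule is needed.

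**7. Would a literal zero go unnoticed?** Hardly. Table 14.3.1.3 would show events under suspected while Table 14.3.1.1 showed no related event. The conflict would be visible within the same set of outputs.

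**The case for a change.** The strongest argument for a change is that an SAP should define each derived variable in terms of what is collected, and this sentence does not. An obvious intent makes a correction easy but does not make it unnecessary. The row will be read: Protocol 4.4 reports related-event incidence for the Phase 2b study by arm (19.7%, 15.9% and 7.9%), so the sponsor itself treats it as a main safety result. If the eCRF in fact used other grades, the sections describing the recorded scale would be wrong, and the documents would still disagree.

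Part of this stands. The wording is inconsistent, this is not an artefact of redaction or text extraction, and no sentence states the mapping for the tables in so many words. What does not follow is that the rule is unusable. It would be, if more than one assignment of the recorded levels were defensible, and step 3 of the working shows that only one is. The Phase 2b percentages show that the row matters to readers. They do not show that its value is in doubt. If the eCRF did carry possibly and probably as grades, the rule would apply to them directly, and the related row would again be determined.

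The point about SAP section 8 carries little weight. SAP 3.5.3–3.5.4 repeat the protocol's scale unchanged, and Protocol 11.8 gives no rule for related events from which SAP 7.6 could depart.

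**Conclusion.** No change is needed. SAP 7.6 uses terms that do not match the recorded scale, but the definitions in Protocol 9.6 and SAP 3.5.3 leave one sensible reading: an event the Investigator records as suspected is counted as related. The mismatch touches one of five items in one summary table, and aligning the words would change neither that count nor any conclusion. The analysis is descriptive, and Protocol 11.7.1 marks hypothesis testing as not applicable.

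This rests on two assumptions. First, the eCRF follows the two-level scale that both documents describe. Second, the events counted carry that scale. The documents do not say which scale the parent study, OTX-101-2016-001, used. However, SAP 7.6 counts as treatment-emergent only events that arise on or after the first dose in the extension, or that worsen after it, so the parent study's scale has little bearing. The documents give no related-event rate for this extension, so the row itself cannot be sized. Its definition is not in real doubt.

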
Methodology: This is an open-label extension of OTX-101-2016-001, a randomized, multicenter, double-masked, vehicle-controlled study in which subjects were randomized to 1 of 2 treatment arms and treated for 12 weeks as follows:
 
 • OTX-101 0.09% (N = ■■■ subjects) • Vehicle (N = ■■■ subjects) 
Subjects successfully completing Study OTX-101-2016-001 may be eligible to enroll in this 40 to 52 week open label extension study in which all subjects will receive OTX-101 0.09% therapy. Subjects may also use unpreserved artificial tears, as needed. Subjects assigned to OTX-101 0.09% in Study OTX-101-2016-001 will participate for 40 weeks. Subjects assigned to vehicle in Study OTX-101-2016-001 are eligible to participate for 52 weeks. Both subject sets will total 52 weeks of participation receiving OTX-101 0.09%.
 
Subjects may enroll in Study OTX-101-2016-002 for up to 14 days following completion of Visit 5 of Study OTX-101-2016-001. At Visit 5a, sites will obtain signed informed consent and dispense study medication. If Visit 5a is not conducted on the same day as Visit 5 of Study OTX-101-2016-001, any female subject of childbearing potential must also have a negative urine pregnancy test. Study “Day” approximately reflects the cumulative number of days of exposure to study drug since the baseline visit of Protocol OTX-101-2016-001, regardless of actual calendar time elapsed.
 
Subjects will self-administer study medication topically to both eyes BID for 40 to 52 weeks depending on their treatment assignment in Study OTX-101-2016-001. Safety evaluations for all subjects will be conducted at study visits on Days 182, 273 and 364; the window for Visits 6 (Day 182) and Visit 7 (Day 273) will be ± 7 days; the window for Visit 8 (Day 364) will be +14 days for those subjects assigned to OTX-101 0.09% in Study OTX-101-2016-001. (± 14 days for subjects assigned to vehicle in Study OTX-101-2016-001, participating for 52 weeks in Study OTX-101-2016-002). Subjects assigned to vehicle in Study OTX-101-2016-001, participating for 52 weeks in Study OTX-101-2016-002, will also be evaluated at Visit 9 (Day 448), which will have a visit window of +14 days. Both eyes will be assessed at each visit. Adverse events and concomitant medications will be documented from signing of informed consent to the subject’s final visit.
	

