11. STATISTICS

11.1. General Considerations

This is an extension of Protocol OTX-101-2016-001 that will evaluate the safety of OTX-101 0.09% ophthalmic solution in subjects with KCS when dosed twice per day for one year.

Subjects in Protocol OTX-101-2016-001 were randomly assigned to OTX-101 0.09% or its vehicle in a 1:1 ratio. However, all subjects enrolling in this extension study will be assigned to OTX-101 0.09%.

A biostatistician will perform statistical analyses as agreed with the Sponsor according to the Statistical Analysis Plan. Any additional or supplemental data analysis performed independently by an Investigator shall be submitted to the Sponsor for review.

No efficacy analyses will be performed. Safety analyses will be performed using the safety analysis population. Definitions for all of the analysis populations can be found in Section 11.5.

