### **2.2. Study Design**

This will be an extension of OTX-101-2016-001, a randomized, multicenter, double-masked, vehicle-controlled study that enrolled male and female subjects, 18 years of age and older, with a patient-reported history of KCS for a period of at least 6 months, a clinical diagnosis of bilateral KCS supported by OTX-101-2016-001 study assessments, and corrected Snellen visual acuity (VA) of better than 20/200 in both eyes at Screening and at Baseline.

Subjects who complete Visit 5 (Day 84) of Study OTX-101-2016-001 may be eligible to enroll in protocol OTX-101-2016-002 within 14 days at the discretion of the Principal Investigator and Sponsor. Subjects who provide written informed consent at Visit 5a and meet the inclusion/exclusion criteria requirements will be enrolled in the study and receive study medication (OTX-101 0.09%). All subjects will participate for at least 40 weeks. Subjects who were randomized to the vehicle arm in Study OTX-101-2016-001 may have the opportunity to participate for an additional 12 weeks, and a total of 52 weeks.

Subjects will self-administer study medication topically to both eyes twice daily (BID) from Visit 5a to Visit 8 (Day 364) or Visit 9 (Day 448). Safety evaluations will be conducted at all study visits. The window for Visits 6 and 7 will be  $\pm 7$  days. The window for Visit 8 will be +14 days for those subjects assigned to OTX-101 0.09% in Study OTX-101-2016-001 ( $\pm 14$  days for subjects assigned to vehicle in Study OTX-101-2016-001, participating for 52 weeks in Study OTX-101-2016-002), and for Visit 9 the window will be +14 days. Both eyes will be assessed at each visit. Adverse events (AEs) and concomitant medications will be documented at each study visit from signing of informed consent to Day 364.

A total of approximately 700 subjects will be enrolled in Protocol OTX-101-2016-001 (approximately 350 subjects in each treatment arm) at approximately 50 clinical sites. Subjects who successfully complete that study may be eligible to participate at the discretion of the Principal Investigator and the Sponsor with the goal of enrolling approximately 300 subjects in Protocol OTX-101-2016-002.

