## **7.5. Treatment Compliance and Exposure**

The % compliance on OTX-101 0.9% will be summarized over all visits by the categories of <70% and  $\geq$ 70%.

Duration of drug exposure will be calculated for each subject as the last date of dosing minus the first date of dosing + 1. The number and percentage of subjects will be summarized according to the following duration-of-exposure categories: '< 3 mon (90 days)', '3 to < 6 mon', '6 mon to < 9 mon', '9 to < 12 mon', and ' $\geq$ 12 mon (360 days)'. A subject data listing will be provided.

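### The AE tables give crude percentages over exposure windows that differ between the two cohorts, so the OTX-101-origin column is not a one-year incidence and no summary table shows when AEs begin

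*SAP*

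**What the plan says.** Protocol 11.1 sets the aim as evaluating safety "in subjects with KCS when dosed twice per day for one year".

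Time in the extension differs by design. The Protocol Synopsis states: "Subjects assigned to OTX-101 0.09% in Study OTX-101-2016-001 will participate for 40 weeks". It then states: "Subjects assigned to vehicle in Study OTX-101-2016-001 are eligible to participate for 52 weeks". SAP 2.2 makes the last part optional: vehicle-origin subjects "may have the opportunity to participate for an additional 12 weeks, and a total of 52 weeks". SAP 5.1 describes the OTX-101-origin cohort as having 12 months on active drug and the vehicle-origin cohort as having at least 9.

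SAP 7.6 starts the treatment-emergent window at the first OTX-101 dose in Study 002. Earlier events count only if they worsen. The planned output is the number and percentage of subjects with an event: an overall summary, then tables by class and preferred term, by maximum intensity and by closest relationship. For the main table, subjects with an event "without regard to intensity, relationship, or seriousness will be tabulated by cohort". Tables 14.3.1.1 to 14.3.1.5 in SAP 10 are all for the whole Safety Population. Onset dates appear in subject listings.

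SAP 7.5 bands time on drug ("The number and percentage of subjects will be summarized according to the following duration-of-exposure categories"), but no AE table uses the bands.

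Protocol 11.5.1.1 defines a One Year Safety Population analysed on combined data from both studies, and Protocol 11.8 merges Study 001 safety data with Study 002. SAP 5 announces three populations, but 5.1 defines only one. SAP 10 lists no one-year table, and SAP 8 reports no changes from the protocol.

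**The concern.** A crude percentage has a clear meaning when everyone is watched for the same stretch of exposure. Here the two columns start at different points on the exposure clock. One has two possible planned end points, and dropouts stay in the denominator with no allowance for time at risk.

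The main question for a long-term safety study is what happens over a year on drug, and whether events fade, persist or begin late. A reader who takes the 12-month label at face value will read about nine months of events as a year's worth. A reader who compares the columns will be comparing different parts of exposure. To see the timing of events, the reader must work through listings.

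**Working it through.** **1. The plan's own figures.** Visit days are from the Schedule of Procedures and the visit headings. Visit 5a is Day 84, Visit 8 is Day 364 and Visit 9 is Day 448.
- To Visit 8: 364 − 84 = 280 days; 280/7 = 40 weeks.
- To Visit 9: 448 − 84 = 364 days; 364/7 = 52 weeks.
- SAP 4 expects at least 150 of about 300 subjects from the OTX-101 arm. With 1:1 allocation (Protocol 11.1), 300 × 1/2 = 150, which reproduces.
- The target of 100 one-year subjects is met from those 150 if 100/150 = 67% are retained.

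The sizing therefore rests on subjects with a full year on drug, but no AE table covers that year.

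**2. What each column covers.**

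| Cohort | Planned days on active drug | Days inside the TEAE window | Exposure weeks covered |
|---|---|---|---|
| OTX-101-origin | 84 + 280 = 364 | 280 (280/364 = 77%) | about 12 to 52 |
| Vehicle-origin, not continuing | 280 | 280 | 0 to 40 |
| Vehicle-origin, continuing | 364 | 364 | 0 to 52 |

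**3. Effect of duration alone (illustration).** The documents give no event rate for this study. Assume a constant hazard and that every vehicle-origin subject continues. Then risk at 364 days = 1 − (1 − risk at 280 days)^(364/280), with 364/280 = 1.30.
- 15%: 1 − 0.85^1.3 = 19.0%, a gap of 4.0 points.
- 20%: 1 − 0.80^1.3 = 25.2%, a gap of 5.2 points.
- 30%: 1 − 0.70^1.3 = 37.1%, a gap of 7.1 points.

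For rare events, working back from 52 weeks with 1 − (1 − p)^(40/52), 1% becomes 0.77% and 2% becomes 1.54%. The gaps are 0.23 and 0.46 points.

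**4. Effect of the optional 12 weeks.** Take a one-year incidence of 10%, which is 7.78% at 40 weeks under the same assumption. The vehicle-origin column then shows 7.8%, 8.9% or 10.0% if 0%, 50% or 100% continue.

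**5. Effect of the different starting points.** If events are front-loaded, the gap in step 3 shrinks, but the starting points matter more. Take the extreme case of an event confined to the first 12 weeks on drug, at the 15.1% seen for instillation site pain on 0.09% in the 12-week Phase 2b trial (Protocol 4.4). The vehicle-origin column would show 15.1%. The OTX-101-origin column would show no new onsets.

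**6. Two checks on any repair.**
- Dividing Study 002 events by all 364 days on drug would understate the OTX-101-origin rate, because only 280/364 = 77% of that time is in the event window. Under a constant hazard the shortfall is about 23%.
- The top band in SAP 7.5 starts at 360 days. Planned exposure ends at 364 days, or 378 with the +14-day window, so a separate 12-month onset interval would hold about 4 to 18 days.

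**7. AE cut-off.** SAP 2.2 has AEs "documented at each study visit from signing of informed consent to Day 364". SAP 3.5.4 collects them up to the last visit. For vehicle-origin subjects, Day 364 is only day 280 on drug, so the first statement would leave out their last 12 weeks.

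**The case against.** The strongest reply is that the study is descriptive, no test between cohorts is planned, and the tables are already split by cohort, so 40 and 52 weeks are not pooled into one percentage. The disposition and exposure tables let a reader see that follow-up is unequal. The Synopsis expects both sets to reach 52 weeks on drug; if they do, the vehicle-origin percentage is close to a one-year figure apart from dropout. All of this stands. It limits the point to the OTX-101-origin window, the optional weeks, dropout and the missing onset tables.

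Three stronger readings are tempting, and the documents do not support them:
- A reader might infer that late AEs are invisible. They are not: Listing 16.2.7 and Table 14.3.2 come from listings ordered by onset date, and narratives are planned. What is missing is a summary table.
- A reader might infer that early instillation-site events will bury a late signal. Preferred terms have their own rows, and the OTX-101-origin window begins after about 12 weeks on drug. Only the any-event line in the vehicle-origin column is open to this.
- A reader might take 4 to 7 points as the expected distortion. That range needs a constant hazard, assumed risks of 15 to 30%, and every vehicle-origin subject continuing.

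**Conclusion.** The point holds as a gap in reporting that should be closed. It does not invalidate an inference, because none is planned. As specified, the OTX-101-origin column is not a one-year incidence: it covers 77% of planned active-drug time and leaves out the first 12 weeks. The vehicle-origin column approximates one only if nearly all subjects continue to Day 448. The two columns should not be compared, and AE timing appears in no summary table.

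The firmest support is internal. The protocol planned a one-year population and a merged dataset that would have dealt with much of this; the SAP contains neither and declares no changes. The coverage figures follow from the visit schedule. The percentage-point figures are illustrative, and the duration gap is smaller if events are front-loaded or rare, or if few subjects continue.

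**What to change.** In SAP 7.6, with matching entries in SAP 5 and 10:

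1. Restore the merged analysis of Protocol 11.5.1.1 and 11.8, so that for OTX-101-origin subjects AEs from the first active dose in Study 001 are included. For vehicle-origin subjects, start the on-drug window at the first Study 002 dose and keep vehicle-period AEs separate. Report events per 100 patient-years on OTX-101, taking events and person-time from the same window. If Study 001 events are not merged, use Study 002 events over Study 002 person-time only.
2. For any TEAE, related TEAEs, SAEs, TEAEs leading to discontinuation and common preferred terms, tabulate incidence by onset interval since first active dose: <3, 3 to <6, 6 to <9, and 9 months or more. The denominator is the number on drug and under AE observation at the start of each interval.
3. Reconcile the end of AE documentation in SAP 2.2 with SAP 3.5.4.
4. Record in SAP 8 any part of the protocol's one-year analysis that is still left out.

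The cost is the Study 001 merge, which the protocol already plans, and one or two tables. AE onset dates are collected (SAP 3.5.4), and dosing dates are needed for SAP 7.5 in any case. Numbers will be smaller in the last interval. Entry requires completing Study 001, so the first interval for OTX-101-origin subjects describes completers only and needs a footnote.
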